**Study design**

The study is an open-label single arm Phase II trial. Eligible patients are those with metastatic hormone-sensitive prostate cancer (mHSPC) or high-risk biochemically recurrent prostate cancer (BCR). All patients must have a documented germline or somatic mutation in a homologous recombination DNA-repair gene (BRCA1, BRCA2, ATM, CHEK2, NBN, BRIP1, RAD50, RAD51C, RAD51D, PALB2, MRE11, FANCA, FANCB, FANCC, FANCD2, FANCE, FANCF, FANCG, FANCI, FANCL, FANCM). Germline genetic testing and molecular sequencing as a screening for eligibility will not be offered. A mandatory tumor biopsy will be performed prior to the start of therapy in all patients with metastatic disease (if tumor material is not successfully obtained at the time of biopsy, then archival material will be sought). A second, OPTIONAL tumor biopsy will take place after three months of therapy.

After enrollment, patients will be treated with rucaparib at the established dose of **600mg by mouth twice daily**. Patients will be followed monthly with clinic visits, safety labs (including CBC w/diff, Comp), PSA, and toxicity assessments. Treatment [with a minimum drug exposure of 12 weeks] will be continued until PSA progression (PCGW3 criteria) or clinical/radiographic progression (whichever comes first), or until unmanageable toxicity requiring drug cessation. Patients who remain on treatment

for >12 months can begin to have their clinic visits, safety labs (including CBC w/diff, Comp), PSA, and toxicity assessments every 3 months.

A trial schema for study treatment appears below:

Criteria for evaluation

Primary Endpoint

- PSA50 response rate, defined as a decline in PSA to  $\geq 50\%$  of baseline level, confirmed with a second measurement at least 4 weeks later (PCWG3).

Secondary Endpoints

- Safety/Tolerability, defined as incidence of CTCAE v5.0 grade  $\geq 3$  toxicities experienced by patients on the trial.
- PSA progression-free survival, defined as a time from initiation on rucaparib therapy until PSA increase of 25%, confirmed with another measurement at least 4 weeks later (PCWG3).
- Radiographic progression-free survival (PCWG3): time to radiographic or clinical progression or death, whichever comes first. Based on RECIST version

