##### *5.8.1 Prohibited before enrollment and during administration of study treatment*

Medications that are prohibited during study treatment and in the prior 6 months prior to enrollments: LHRH agonist / antagonist therapy, androgen receptor antagonists, and androgen synthesis inhibitors. 5-alpha reductase inhibitors are allowed if subject has been taking stable dose of medication for prior 6 months.

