### 6.4 Removing Patients from the Protocol

In the absence of treatment delays because of adverse events, treatment will continue for until one of the following criteria applies:

- Patient decision. The patient is at any time free to discontinue treatment, without prejudice to further treatment
- Severe non-compliance with the study protocol
- Bone marrow findings consistent with myelodysplastic syndrome (MDS)/acute myeloid leukaemia (AML)
- Potential Hy's Law cases (AST or ALT  $\geq 3 \times$  ULN and TBL  $\geq 2 \times$  ULN with no other reason)
- PSA doubling from baseline value, confirmed by a second value at least 4 weeks apart, with a minimum time since initiation of therapy of 12 weeks.
- Disease progression by symptomatic or radiographic assessment. Patient requiring palliative radiation therapy will be considered to have disease progression and removed from the study.
- Intercurrent illness that prevents further administration of treatment
- Unacceptable adverse events that may or may not be directly related to treatment but that, in the judgment of the treating physician, makes it dangerous for the patient to be retreated.
- Adverse events requiring cessation of rucaparib, with inability to restart therapy within 14 days.
- General or specific changes in the patient's condition that render the patient unacceptable for further treatment, in the judgment of the investigator

Because an excessive rate of withdrawals can render the study uninterpretable, unnecessary withdrawal of patients should be avoided. When a patient discontinues treatment early, the investigator should make every effort to contact the patient and to perform a final evaluation. The reason(s) for withdrawal should be recorded.

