### **8.4.2 PSA**

Per the PCWG3, PSA progression is defined as the date that a 25% or greater increase and an absolute increase of 2 ng/mL or more from the nadir is documented and confirmed by a second value obtained 3 or more weeks later. Where no decline from baseline is documented, PSA progression is defined as a 25% increase from the baseline value along with an increase in absolute value of 2 ng/mL or more after 12 weeks of treatment.

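### The synopsis stops rucaparib at PCWG3 PSA progression, Section 6.4 only at confirmed PSA doubling from baseline, and nothing says which governs

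*Combined protocol and SAP*

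**What the plan says.** In the synopsis (Study design), rucaparib has a 12-week minimum exposure, and treatment "will be continued until PSA progression (PCGW3 criteria) or clinical/radiographic progression (whichever comes first), or until unmanageable toxicity requiring drug cessation".

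Section 6.4 introduces its list by saying that "treatment will continue for until one of the following criteria applies". The only PSA criterion is "PSA doubling from baseline value, confirmed by a second value at least 4 weeks apart". That criterion cannot be applied until 12 weeks after the start of treatment. The disease-progression bullet covers symptomatic and radiographic progression, not PSA. Other bullets let the patient stop at any time and let the investigator stop for changes in the patient's condition. The section closes by asking that "unnecessary withdrawal of patients should be avoided".

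PSA progression is itself defined in two ways.
- Sections 8.1.2.2 and 8.4.2 have a 2 ng/mL floor. After a decline, 8.4.2 asks for a rise of at least 25% together with this: "an absolute increase of 2 ng/mL or more from the nadir is documented and confirmed by a second value obtained 3 or more weeks later". For men whose PSA never fell, it says: "Where no decline from baseline is documented, PSA progression is defined as a 25% increase from the baseline value", again with a rise of at least 2 ng/mL, after 12 weeks.
- The synopsis (secondary endpoints and statistical method), Section 2.2 and Section 10.1.2.2 give a 25% rise confirmed at least 4 weeks later, with no floor.

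Sections 8 and 10 use these as endpoint definitions and do not tell a site to stop the drug. No text ranks the synopsis against the body.

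**The concern.** A site needs one instruction for when a rising PSA ends treatment. The two given here differ in reference point (nadir or baseline) and in size (25% or 100%). With two sites, each could follow a different rule in good faith.

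Three things depend on the answer:
- How long a man stays on rucaparib after PSA progression, and so how much exposure and toxicity is accrued.
- When the protocol obliges him to stop. Section 5.8.1 reads "Medications that are prohibited during study treatment and in the prior 6 months prior to enrollments: LHRH agonist / antagonist therapy", with androgen receptor antagonists and androgen synthesis inhibitors alongside, while the rationale names ADT as the option on progression.
- How long he is scanned. Notes b and d to Table 1 tie scans to enrollment, with at most an off-treatment scan and no routine later visit except for toxicity. Section 10.1.2.3 censors radiographic PFS at the last scan without progression.

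**Working it through.** **The plan's own figures.** None bears on the stopping rule. For completeness, the Simon design (stop at 6 or fewer of 12; promising at 18 or more of 28) was recomputed by exact binomial. Early stopping at a 50% rate is 0.613 (stated 0.61), type I error 0.0815 (limit 0.1), and power at 75% is 0.902 (stated 90%). The removal rule is not an input to any of these.

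**Thresholds.** Let B be baseline and N the nadir, with N = B if there is no decline.
- Section 8.4.2: max(1.25N, N + 2).
- 25%-only wording, measured from nadir: 1.25N.
- Section 6.4: 2B.

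| B (ng/mL) | N | 8.4.2 | 25% only | 6.4 |
|---|---|---|---|---|
| 10 | 10 | max(12.5, 12) = 12.5 | 12.5 | 20 |
| 10 | 5 | max(6.25, 7) = 7 | 6.25 | 20 |
| 4 | 4 | max(5, 6) = 6 | 5 | 8 |
| 2.0 | 2.0 | max(2.5, 4) = 4 | 2.5 | 4 |

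For B of at least 2.0, the screening minimum, N + 2 ≤ B + 2 ≤ 2B and 1.25N < 2B. Doubling therefore never comes first, and it ties with 8.4.2 only at B = N = 2.0. PSA is redrawn on day 1 if screening labs are more than 7 days old, so a baseline just under 2.0 is possible. At 1.8, 8.4.2 gives 3.8 against 3.6 for doubling; the 25%-only wording gives 2.25.

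**Time, no decline, B of 8 or more.** From B = 8 upward, 1.25B ≥ B + 2, so both definitions give 1.25B. Assume a constant doubling time D in months. Both rules carry the 12-week minimum, 84/30.4 = 2.76 months.
- PCWG3 time = max(D × log2(1.25), 2.76) = max(0.322D, 2.76).
- Doubling time point = max(D, 2.76).

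| D | PCWG3 | Doubling | Gap (months) |
|---|---|---|---|
| 3 | 2.76 | 3 | 0.24 |
| 6 | 2.76 | 6 | 3.24 |
| 9 | 2.90 | 9 | 6.10 |

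Nine months is the entry limit for biochemical recurrence in the synopsis; 3 and 6 are assumptions. The documents give no on-treatment doubling time. On 28-day visits the thresholds are first seen at weeks 12 and 16, 12 and 28, and 16 and 40. If the week-12 visit does not count as after 12 weeks, the first pair becomes 16 and 16.

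**Time, no decline, B below 8.** With the 2 ng/mL floor the gap shrinks. At B = 4, log2(6/4) = 0.585, the PCWG3 times are 2.76, 3.51 and 5.26 months, and the gaps are 0.24, 2.49 and 3.74. At B = 2.0 the gap is zero. With the 25%-only wording the ratio stays at 2/1.25 = 1.6, so the gaps remain 0.24, 3.24 and 6.10 at every baseline.

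**Left out.** No months are given for men whose PSA first falls. Confirmation is also excluded: 6.4 asks for a second value at least 4 weeks later, 8.4.2 states none when there was no decline, and the 25%-only wording requires one. Removal could shift by a further visit.

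**Endpoints.**
- PSA50: the rules give different results only for a man who meets PCWG3 progression and then, still on drug, has a confirmed 50% fall from baseline. I judge that to be rare.
- PSA-PFS: with B of at least 2.0 the event comes no later than doubling, so its date is the same under either rule.
- Radiographic PFS: scans run every 3 cycles (metastatic) or 6 cycles (biochemical recurrence) while enrolled. The earlier stop ends imaging sooner and can censor a man soon after his PSA signal.

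**The case against.** Doubling may be deliberate. Section 6.4 warns against excessive withdrawals, and Section 8.2.1 discourages decisions on PSA alone in the first 12 weeks. That stands as far as it goes: the documents do not reveal the intent, and a looser rule is defensible. But the synopsis sentence would then be wrong, and Section 8.2.1 settles nothing after week 12.

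The month figures can also be attacked, with reason. Metastatic patients are scanned every 3 cycles, so scans fall inside the windows of weeks 12 to 28 and 16 to 40, and patient choice or investigator judgment can intervene at any time. The figures are upper limits, not expected delays.

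Site calls every 3 months and at least quarterly data review might reveal divergent practice. They would not tell a site which rule is right.

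Three stronger readings are tempting, and the documents do not support them:
- That the doubling rule fixes the earliest date for ADT. Section 6.4 lets a man leave at any time, and Section 3.3 admits only men who are ineligible for ADT or have declined it. Only the protocol-mandated stop moves.
- That the primary result or the Simon design is compromised. Neither depends materially on this rule.
- That the rationale (synopsis and Section 1.3.1), which takes non-responding metastatic men off study at the earliest indication of progression, decides the matter. It does not define progression by PSA. It fits the earlier rule better, but that supports a preference only.

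**Conclusion.** The contradiction is in the text and needs no assumption: two PSA stopping rules with no order of precedence. Its size does rest on assumptions. The gap of up to about 0.2, 3.2 or 6.1 months applies to a man with no decline and a baseline of at least 8 ng/mL, under constant PSA growth, with the 12-week minimum in both rules and no earlier stop for another reason. Below 8 ng/mL the gap either shrinks to zero at 2.0 or does not shrink, depending on which PSA-progression definition is applied. A reader should not conclude either that low baselines are harmless or that they are fully affected until one definition is chosen.

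The consequences are for exposure, toxicity accrual, the mandated stop and the length of radiographic PFS follow-up before censoring. The point is worth an amendment because it governs when patients stop the drug.

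**What to change.** State one PSA removal rule in both places. Preferably, replace the doubling bullet in Section 6.4 with PSA progression as defined in Section 8.4.2, after a minimum of 12 weeks on drug, and cite 8.4.2 in the Study design paragraph of the synopsis. The citation is needed because the synopsis otherwise keeps its own definition without the 2 ng/mL floor. If the sponsor intends doubling, amend the synopsis sentence instead and leave 6.4 as it is.

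Either way the administrative cost is a short wording amendment and a notice to the two sites, with no added patients, visits or scans. The preferred option has a scientific cost: some men stop earlier, which shortens radiographic PFS imaging follow-up and brings censoring forward. The sponsor should weigh that against the longer exposure under the doubling rule.

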## 7. ADVERSE EVENTS

## 7.1 Definitions

### 7.1.1 *Adverse Event (AE)*

An AE is defined as any untoward medical occurrence in a patient administered a medicinal product that does not necessarily have a causal relationship with this treatment. An AE can, therefore, be any unfavorable and unintended sign (including an abnormal laboratory finding), symptom, or disease temporally associated with the use of an investigational product, whether or not related to the investigational medicinal product. This includes an exacerbation of pre-existing conditions or events, intercurrent illnesses, drug interaction, or the significant worsening of the indication under investigation that is not recorded elsewhere on the eCRF under specific efficacy assessments. Anticipated fluctuations of pre-existing conditions, including the disease under study, that do not represent a clinically significant exacerbation or worsening are not considered AEs.

It is the responsibility of the investigator to document all AEs that occur during the study. AEs should be elicited by asking the patient a non-leading question (eg, "Have you experienced any new or changed symptoms since we last asked/since your last visit?"). The existence of an AE may be concluded from a spontaneous report of the patient; from the physical examination; or from special tests such as the ECG, laboratory assessments, or other study-specified procedure (source of AE).

Symptoms reported spontaneously by the patient during the physical examination would also qualify as an AE (and hence documented on the AE eCRF, not on the physical examination eCRF, which is reserved for physical signs or findings).

### 7.1.2 *Serious Adverse Event (SAE)*

An SAE is any untoward medical occurrence that occurs at any dose (or, occurs after informed consent is given and prior to dosing if the SAE is related to a study procedure) that:

- Results in death. Any event resulting in death during the reporting period (from date of first dose of study drug through 28 days after last dose) must be treated as an SAE and reported as such. An event related to a study procedure that occurs after informed consent, but prior to dosing that results in death must also be reported as an SAE.
- Is life-threatening (patient is at immediate risk of death from the event as it occurred)
- Requires in-patient hospitalization (formal admission to a hospital for medical reasons) or prolongation of existing hospitalization
- Results in persistent or significant disability/ incapacity
- Results in a congenital anomaly or birth defect

Important medical events that may not result in death, are not life-threatening, or do not require hospitalization may be considered SAEs when, based on appropriate medical judgment, they may jeopardize the patient and may require medical or surgical intervention to prevent one of the outcomes listed in this definition. Examples of such events include allergic bronchospasm requiring intensive treatment in an emergency room or at home or the development of drug dependency or drug abuse.

#### *7.1.2.1 Events or Outcomes Not Qualifying as Serious Adverse Events*

The following are not considered SAEs and therefore do not need to be reported as such:

- Pre-planned or elective hospitalization including social and/ or convenience situations (eg, respite care)
- Hospital visits of less than 24 hours duration (eg, patient presents to the emergency room, but is not admitted to a ward)
- Overdose of either Clovis study drug or concomitant medication unless the event meets SAE criteria (eg, hospitalization). However, the event should still be captured as a nonserious AE on the appropriate eCRF page
- Events of progression of the patient's underlying cancer as well as events clearly related to progression of the patient's cancer (signs and symptoms of progression) should not be reported as a serious adverse event unless the outcome is fatal within the safety reporting period. If the event has a fatal outcome within the safety reporting period, then the event of Progression of Disease must be recorded as an AE and as a SAE with CTCAE Grade 5 (fatal outcome) indicated.

#### *7.1.3 Medical significance*

An event that is not fatal or life-threatening and that does not necessitate hospitalization may be considered serious if, in the opinion of the investigator, it jeopardizes the patient's status and might lead to medical or surgical intervention to prevent any of the outcomes described in section 7.1.2. Such medically significant events could include allergic bronchospasm requiring intensive treatment in the emergency room or at home, blood dyscrasias that do not result in inpatient hospitalization, or the development of drug dependency or abuse.

#### *7.1.4 Adverse Events of Special Interest (AESI)*

AESIs (serious or nonserious) are defined as AEs of scientific and medical concern specific to the sponsor's product or program, for which ongoing monitoring and rapid communication by the investigator to the sponsor can be appropriate. Such an event might warrant further investigation in order to characterize and understand it. Depending on the nature of the event, rapid communication by the trial sponsor to other parties (eg, regulators) might also be warranted.

Details on the sponsor's currently agreed list of AESIs for rucaparib can be found in the current rucaparib IB. These AESIs are to be reported to the sponsor expeditiously.

**7.1.5 *Progression of malignancy***

Progression of a patient's malignancy should not be considered an AE or SAE, unless in the investigator's opinion, study treatment resulted in an exacerbation of the patient's condition. If disease progression results in death or hospitalization while on study or within 28 days of the last dose, progressive disease will be considered an SAE.

**7.1.6 *Life-threatening events***

A life-threatening event is any AE that places the patient at immediate risk of death from the reaction as it occurs. It is not a reaction that had it occurred in a more severe form, might have caused death.

**7.1.7 *Hospitalization or prolongation of hospitalization***

Hospitalization encompasses any inpatient admission (even for less than 24 hours) resulting from a precipitating, treatment-emergent adverse event. For chronic or long-term patients, inpatient admission also includes transfer within the hospital to an acute or intensive care inpatient unit. Hospitalizations for administrative reasons or a non-worsening preexisting condition should not be considered AEs (e.g. admission for workup of a persistent pretreatment laboratory abnormality, yearly physical exam, protocol-specified admission, elective surgery). Preplanned treatments or surgical procedures should be noted in the baseline documentation. Hospitalization because of an unplanned event will be deemed an SAE.

Prolongation of hospitalization is any extension of an inpatient hospitalization beyond the stay anticipated or required for the original reason for admission.

**7.1.8 *Significant disability***

Disability is a substantial disruption of the patient's ability to conduct normal life functions.

**7.1.9 *Pregnancy***

Male participants should refrain from fathering a child or donating sperm during the study and for 6 months following the last dose.

Pregnancy of the patient's partners is not considered to be an adverse event. However, the outcome of all pregnancies (spontaneous miscarriage, elective termination, ectopic pregnancy, normal birth or congenital abnormality) should if possible be followed up and documented.

The outcome of any conception occurring from the date of the first dose until 6 months *after the last dose* should be followed up and documented.

All outcomes of pregnancy should be reported to Clovis Oncology.

**7.1.10 *Deaths***

All deaths that occur during the study, or within the protocol-defined 30-day post-study follow-up period after the administration of the last dose of study treatment, must be reported as follows:

Death that is clearly the result of disease progression should be reported to the study monitor at the next monitoring visit, be documented, and reported as an SAE.

Where death is not due (or not clearly due) to progression of the disease under study, the AE causing the death must be reported to the study monitor as a SAE within **24 hours**. The report should contain a comment regarding the co-involvement of progression of disease, if appropriate, and should assign main and contributory causes of death.

Deaths with an unknown cause should be reported as a SAE, but followup should be done to determine the cause of death. If a cause of death is determined, the event term of "death" must be updated at that time. A post mortem maybe helpful in the assessment of the cause of death, and if performed a copy of the post-mortem results should be forwarded to Clovis Oncology within the usual timeframes.

The most recent version of the NCI CTCAE v.5.0 handbook will be used for adverse event descriptions and grading.

All AEs (including SAEs and AESIs) occurring during the study are to be followed up in accordance with good medical practice until resolved; judged no longer clinically significant; or, if a chronic condition, until fully characterized through 28 days after the last dose of study drug. Any SAEs, AESIs, and treatment-related Grade 3/4 AEs must be followed until resolution or stabilization, or until lost to follow-up. After the 28-day window, treatment-related SAEs and all AESIs, irrespective of causality, need to be reported.

## 7.2 **Expectedness**

Adverse events can be considered, "expected," or, "unexpected."

### 7.2.1 *Expected Adverse Events*

Expected adverse events are those that have been previously identified as resulting from administration of the agent. An adverse event can be considered expected when it appears in the same nature severity and specificity as what is in the current adverse event list of the Investigator's Brochure (Reference Safety Information [RSI] section).

